A non-flat dose response relationship will be established if at least one model is statistically significant, rejecting the null hypothesis of a flat dose response relationship jointly over the candidate dose response models, with a contrast test controlled for the family-wise type I error rate at one sided  $\alpha = 5\%$ .

If a non-flat dose-response relationship is established, the statistically significant (best fitting) model(s) from the above candidate set will be refitted to the data to generate new estimates for all model parameters from the data. The target dose(s) will be estimated from the best fitting model(s) by incorporating information on the minimum clinically relevant effect (“delta”) and accounting for safety.

The primary analysis will be performed using the FAS, as defined in [Section 7.2.1](#).

The primary MCPMod analysis will use the actual maintenance dose (i.e., as treated). Actual maintenance dose is defined as the dose the patient was receiving at the start of the maintenance period (which is expected to be one of the planned maintenance doses). Rules for handling any special situations (e.g., any patient who was not receiving the same dose at the end of the maintenance period as at the start of the maintenance period) will be addressed in the TSAP. Any patient who discontinued treatment prior to starting the maintenance period will be assigned to the next target maintenance dose up from the last dose which was tolerated during the dose escalation period. For example, if a patient was randomised to a

maintenance BI 456906 dose of 6.0 mg and discontinued during the dose escalation period, having tolerated a dose of 2.4 mg but not tolerated a dose of 3.0 mg, this patient will be assigned to an actual maintenance dose of 4.8 mg in the analysis.

A sensitivity MCPMod analysis will be performed which uses randomised maintenance dose, irrespective of whether this dose was reached/tolerated. [REDACTED]

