## 7.5 DETERMINATION OF SAMPLE SIZE

Calculations were performed using R Version 3.6.1.

One aim of this trial is to show a significant non-flat dose-response curve across the different doses and placebo. Additionally to that, at least one modelled dose within the dose range considered should show a benefit of at least "delta" in the primary endpoint responder rate compared to placebo. The probability of success of this trial is therefore defined as the probability to (1) obtain a significant test for non-flat dose-response curve and (2) to observe for at least one of the modelled doses an effect difference of at least delta compared to placebo.

The sample size calculation is based on an assumed maximum difference in the primary endpoint responder rate (BI 456906 vs. placebo) of 25%, as well as on the pre-specified models listed in [Section 7.2.2](#). For placebo, a response rate of 20% at Week 48 will be considered [[R16-5487](#); [R16-5489](#); [R18-2781](#)].

Using a total sample size of 240 evaluable patients (60 per treatment group), the probability of a successful trial (as defined above) was estimated using simulations. For each dose group, samples of the required size were drawn from a binomial distribution.

Based on these assumptions, the success probability under a delta of 20% (i.e., non-flat curve achieved, and at least one BI 456906 dose shows a difference to placebo of at least 20%) is approximately 76% when assuming a linear dose response curve. Assuming a different form

for the underlying dose response curve (Emax, exponential, quadratic), the success probability is between 73% and 82% (data not shown). For a delta of 10% the respective success probability is 92% assuming a linear dose response shape, and between 92% and 95% for the other dose response shapes (data not shown).

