The multiple comparison procedure will be implemented using contrast tests which control the family-wise type I error rate at a one-sided $\alpha = 0.05$. Candidate models will be used as described in the CTP Section 7.2.2, that is:

- Linear
- Exponential1: 25% of maximum effect achieved at dose 3.0 mg (note: this dose is used for model specification only, it was not included in the trial)
- Exponential2: 5% of maximum effect achieved at dose 3.0 mg
- Emax1: 50% of maximum effect achieved at dose 3.0 mg
- Emax2: 80% of maximum effect achieved at dose 3.0 mg
- Quadratic: Maximum effect achieved at dose 4.8 mg.

For the MCPMod test, the contrast coefficients of each candidate model will be calculated using the R-function ‘optContr’ based on observed results from the logistic regression (with Firth bias reduction if used), that is, the variance-covariance matrix from the logistic regression step will be used as input to ‘optContr’.

If at least one dose-response model is statistically significant, the null hypothesis of a flat dose-response curve can be rejected indicating a benefit of Survodutide over placebo.

All dose-response models will be re-fitted to the data (irrespective of statistical significance in the previous step) without any parameter assumptions to generate a set of new estimates of the model parameters. For all significant models, the generalised Akaike Information Criterion (AIC) will be calculated and reported in the displays. The final model will be chosen as the model with the best fit according to AIC, that is, the model with the smallest AIC value.

The target dose for MCPMod purposes is defined as the smallest Survodutide dose which is estimated to achieve an absolute improvement in the proportion of patients with a histological improvement based on liver biopsy after 48 weeks of treatment of 20% or more compared with placebo. If no dose within the range studied by the trial meets this criterion, then it will be concluded that MCPMod has not identified a target dose.

Estimates for each dose group will be calculated and will be based on the final dose-response model. In practice, the choice of the target dose to be investigated in Phase 3 will be based upon efficacy as well as considering tolerability and safety and other relevant information.

The following tables and displays are planned:

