- Table of the contrast coefficients per dose group and candidate model, together with the MCPMod test statistics and p-values for each model, and the critical value.
- For all models fitted to the observed data: Figure of the fitted dose-response curve plus 95% confidence band overlayed with adjusted mean and corresponding 95% confidence interval per dose (estimated from the logistic regression (with Firth bias reduction if used)) – this figure is plotted on the logit scale.
- For all models fitted to the observed data: Figure of the fitted dose-response curve plus 95% confidence band overlayed with adjusted mean and corresponding 95%

confidence interval per dose (estimated from the logistic regression (with Firth bias reduction if used)) – this figure is plotted on the probability scale (figure converted from logit-scale to probability scale).

The predicted Survodutide dose which achieved a 20% improvement in absolute responder proportions compared with placebo will be annotated onto the above figures on the probability scale for the significant model shapes (Linear, Exponential, Emax and Quadratic).

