The multiple comparison procedure will again be implemented using contrast tests which control the family-wise type I error rate at a one-sided $\alpha = 0.05$. The same candidate models will be used as those used for the primary endpoint MCPMod analysis (described in [Section 7.4.1](#)), and the same method will be used to calculate the contrast coefficients.

If at least one dose-response model is statistically significant, the null hypothesis of a flat dose-response curve can be rejected indicating a benefit of Survodutide over placebo.

All dose-response models will be re-fitted to the data (irrespective of statistical significance in the previous step) without any parameter assumptions to generate a set of new estimates of the model parameters. For all significant models, the generalised AIC will be calculated and reported in the displays. The final model will again be chosen as the model with the best fit (smallest AIC).

Estimates for each dose group will be calculated and will be based on the final dose-response model. No target dose criterion was pre-specified for the MRI-PDFP responder secondary endpoint.

Similar tables and figures will be used to display the results of the MCPMod analysis as were described in [Section 7.4.1](#).

The above analysis will be performed on the TS using both actual maintenance treatment and planned maintenance treatment. In both cases, all post-baseline MRI-PDFP data within the Week 48 visit window will be used, both on- and off-treatment.

MRI-PDFF continuous secondary endpoints - main analysis

Descriptive summaries of liver fat content (measured in units of % using MRI-PDFF), as well as absolute and percentage changes from baseline, will be presented over time. These will be produced on the TS for both actual maintenance treatment and planned maintenance treatment, and will include both on- and off-treatment data in the relevant visit windows. The

descriptive summaries will be produced overall, and further split by presence of any type of diabetes (Yes, No).

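### Dose estimates from the single smallest-AIC model carry a 95% band that ignores model selection; at 2.4 or 4.8 mg it covers only about 76-84% under four of the six planned dose-response shapes

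*SAP*

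**What the plan says.** SAP 7.4.1 tests six candidate shapes, then refits every model with free parameters. One model is kept: "The final model will be chosen as the model with the best fit according to AIC". It continues: "Estimates for each dose group will be calculated and will be based on the final dose-response model". The target dose is defined there as the smallest dose estimated to give at least 20 percentage points over placebo. That definition names no model, but it follows directly on the final-model rule.

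The interval on each model is described under the planned displays: "Figure of the fitted dose-response curve plus 95% confidence band overlayed with adjusted mean". These figures are planned for all fitted models. They overlay the per-dose logistic-regression estimates with 95% intervals, and on the probability scale they mark the 20-point dose for each significant shape.

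SAP 7.5.2 repeats the AIC rule for the MRI-PDFF responder endpoint. Protocol 7.2.2 speaks of best-fitting models in a form that allows more than one; the SAP narrows this to one. No averaging, bootstrap or other allowance for selection appears in the readable text of either document.

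**The concern.** Characterising the dose response is a main objective (Protocol 2.1.1), and the trial is meant to inform the phase III dose. A model's own band is valid if that model was fixed beforehand. Here the data choose it, from four dose levels with 60 patients each. The line has two parameters and the other families three, so the line wins AIC unless a curve improves the fit by more than 2 units. With this little information it often wins when it is wrong. Its band is then both narrow and off-centre, and the reader sees it labelled 95%. The target dose has no planned interval at all.

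**Working it through.** **Inputs.** One-sided family-wise 5%, logit scale, six candidate shapes, smallest AIC, 20-point target (SAP 7.4.1); 240 patients, 60 per group, and "For placebo, a response rate of 20% at Week 48 will be considered" (Protocol 7.5); 45% maximum (Protocol 7.2.2). Assumed, because the documents do not give them: no covariates, diagonal covariance, and fit bounds for ED50 (0.001-1.5) and the exponential parameter (0.1-2), both as multiples of the top dose.

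**Method.** Binomial draws at 0, 2.4, 4.8 and 6.0 mg; optimal contrasts with critical value 1.956; generalised least squares on the logits; AIC = Σw(y − f)² + 2k, with w = n·p(1 − p), k = 2 for the line and 3 otherwise; delta-method 95% band of the selected model.

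**Reproducing Protocol Table 7.5:1.** Linear truth, 20% vs 45%, delta 20: 92.8% positive MCP test and 76.6% success (stated 92.1% and 75.9%). For 20% vs 50%: 98.1% and 91.8% (stated 97.9% and 90.9%). Flat: 4.3% and 0.3% (stated 4.5% and 0.2%). All agree within 2 points.

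**Hand check under Emax2** (80% of maximum effect at 3.0 mg, so 3/(ED50 + 3) = 0.8 and ED50 = 0.75).
- logit(0.20) = −1.386 and logit(0.45) = −0.201, a span of 1.186.
- At 2.4 mg the share of the 6.0 mg effect is (2.4/3.15)/(6/6.75) = 0.857. The true logit is −1.386 + 0.857 × 1.186 = −0.370, a response of 40.9%.
- The weights 60·p(1 − p) are 9.6, 14.5, 14.8 and 14.85. The weighted line through the true logits is −1.096 + 0.1735·d, which gives −0.680 at 2.4 mg, or 33.6%.
- Bias is −0.680 + 0.370 = −0.310; the line's standard error there is 0.157; the ratio is −1.98. A nominal 95% band would cover Φ(1.96 + 1.98) − Φ(−1.96 + 1.98) ≈ 49%, before any selection.
- The line's weighted lack of fit is 2.53. Against one three-parameter rival, AIC keeps the line with probability P(|Z + √2.53| < √2) ≈ 43%.

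So the line is wrong at 2.4 mg by about two standard errors, and AIC still cannot reliably reject it.

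**Simulation, significant trials only** (3,000 to 20,000 trials per shape; ranges are across runs).

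| True shape | Line selected | Lowest coverage of selected model's band |
|---|---|---|
| Linear | – | about 93-94% |
| Exp1 | 64% | about 90% at 2.4 mg (about 91% at 4.8 mg) |
| Exp2 | 30% | 80-82% at 4.8 mg |
| Emax1 | 59% | 84% at 2.4 mg |
| Quadratic | 42% | 82-84% at 2.4 mg |
| Emax2 | 35-36% | 76-78% at 2.4 mg |

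Under Emax2, coverage at 2.4 mg by selected family is 39.9% (line), 33.7% (exponential), 99.7% (Emax) and 96.0% (quadratic). Weighting by selection shares: 0.351 × 0.399 + 0.006 × 0.337 + 0.334 × 0.997 + 0.309 × 0.960 = 0.77. The line accounts for nearly all the loss.

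**Controls.** With the true family fitted and no selection, coverage is about 95-99%. The per-dose intervals cover about 94-98%. The loss therefore comes from the model step and not from small samples.

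**Target dose.** Under Emax2 the true 20-point dose is about 2.1 mg. The single-model estimate runs from 0.1 to 5.1 mg (10th to 90th percentile).

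**Bootstrap averaging.** Coverage was 94-98% in all six shapes (500 trials × 300 resamples), 94-99% in the four shapes of a second run (1,000 × 400), and about 92-97% in a third. Target-dose RMSE fell in all six shapes, modestly: about 1.28 to 1.18 mg (linear) and 1.7 to 1.5 mg (Emax1).

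**The case against.** The strongest reply is that the SAP does not hide model uncertainty. It draws every fitted model with its band, overlays logistic intervals that are well calibrated, and marks the 20-point dose for every significant shape. It also reports odds ratios with 95% intervals. This stands, and it limits the defect to the final-model estimates, their band and one target dose. What is missing is a rule for combining curves that disagree.

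A reader might infer that the 95% band covers only about 76% in general. It does not. That figure belongs to one shape at one dose, and most cells lie at about 90-95%. Emax2 also puts about 41% response at 2.4 mg, while Protocol 1.4.1 and 4.1.2 expect that dose to act much like placebo on NASH. But Emax2 is one of the sponsor's own candidates. Exp2, which does keep 2.4 mg near placebo, gives 80-82% at 4.8 mg.

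A reader might also infer that the phase III dose would be chosen wrongly. The documents do not support this: SAP 7.4.1 bases that choice on tolerability, safety and other information as well, Protocol 7.1 calls the testing exploratory, and no probability of a wrong dose was calculated. Nor are the selected estimates worse than raw proportions: in one check their RMSE was no larger at any active dose (Emax2, 2.4 mg: 6.4 vs 6.4 points).

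**Conclusion.** The concern holds in this limited form. The selected model's nominal 95% band falls clearly short at 2.4 mg under Emax2, Emax1 and quadratic truth and at 4.8 mg under Exp2, with coverage of about 76-84%. Elsewhere it is mostly about 90-95%. The MCP test and its type I error are not affected.

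The figures assume 60 per arm, no diabetes or fibrosis covariates and the stated fit bounds. Analysis by actual maintenance dose may change the arm sizes. Parts of Protocol 7.2.2 and other analysis text are redacted, so an averaging analysis there cannot be excluded; none is visible. Coverage for the MRI-PDFF endpoint (15% vs 50%) was not simulated, and SAP 7.5.2 sets no target dose for it, so the size found here should not be carried over.

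**What to change.** In SAP 7.4.1, derive the dose-group estimates, the 95% band and the 20-point target dose by bootstrap model averaging over the significant models. Resample the logit estimates from their covariance matrix, refit, select by AIC within each resample, and report the median curve with percentile limits. Keep the single-model fits and the existing figures as supportive. The same wording can go into 7.5.2 for consistency.

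The cost is SAP text, slightly more programming, and bands on average up to about 30-36% wider at the tested doses. Trial conduct does not change, and failure to find a target dose did not become more frequent with the bootstrap.

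AIC-weighted averaging is a different method and its figures should not be borrowed. It lowers target-dose RMSE further under linear truth (about 1.27 to 1.05 mg), but its coverage drops to 90% at worst (Exp2, 4.8 mg) and it finds no target dose more often.

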7.4.2 Sensitivity analysis, subgroup analysis, exploratory analysis of the primary endpoint(s)

Sensitivity analysis

The analysis of the primary endpoint specified in [Section 7.4.1](#) will be repeated for the following, using the same model for estimation (logistic regression with Firth bias reduction if necessary) unless otherwise specified, with the same model terms, and using the same subsequent MCPMod procedure:

- Planned maintenance treatment; using all post-baseline biopsy data (as above)

7.5 SECONDARY ENDPOINT(S)

7.5.1 Key secondary endpoint(s)

This section is not applicable as no key secondary endpoint has been specified in the protocol.

7.5.2 Secondary endpoint(s)

MCPMod dose finding analyses will only be performed for secondary endpoints where specified below. [REDACTED]

MRI-PDFF responder secondary endpoint - main analysis

Frequency tables will be produced of the MRI-PDFF responder secondary endpoint (percentage reduction of at least 30% from baseline in liver fat content, measured in units of % using MRI-PDFF, after 48 weeks of treatment) in both of the following ways:

- TS, actual maintenance treatment, using all post-baseline MRI-PDFF data within the Week 48 visit window (see [Section 6.7](#)), both on- and off-treatment (see [Section 6.1.6](#))
- TS, planned maintenance treatment, using all post-baseline MRI-PDFF data within the Week 48 visit window, both on- and off-treatment.

The above frequency tables will be displayed similarly to those for the primary endpoint.

The frequency tables will be produced overall, and further split by each of the subgroups defined in [Section 6.4](#).

Similarly to the primary endpoint analysis described in [Section 7.4.1](#), a logistic regression will first be performed on the MRI-PDFF responder secondary endpoint to estimate the treatment effects of the Survodutide doses and placebo, together with the corresponding variance-covariance matrix. The MCPMod approach will then use these estimates to test for a non-flat dose response curve and to identify suitable dose-response shapes out of a selection of candidate models.

The logistic regression model will be fitted without an intercept, and will include presence of diabetes of any type [yes, no], baseline fibrosis score [F1, F2, F3] and the dose group as factors, and baseline liver fat content (assessed by MRI-PDFF) as a continuous linear covariate. In the case that 0 events are observed in any combination of dose group and strata, the Firth bias reduction method will again be used. The subsequent MCPMod analysis will again be fully carried out on the logit scale, with conversion from the logit scale to the probability scale for interpretation.

A summary table will be produced of the logistic regression results, including estimated odds ratios for the comparison of each Survodutide dose against placebo and their 95% confidence intervals and associated p-values.

The multiple comparison procedure will again be implemented using contrast tests which control the family-wise type I error rate at a one-sided $\alpha = 0.05$. The same candidate models will be used as those used for the primary endpoint MCPMod analysis (described in [Section 7.4.1](#)), and the same method will be used to calculate the contrast coefficients.

If at least one dose-response model is statistically significant, the null hypothesis of a flat dose-response curve can be rejected indicating a benefit of Survodutide over placebo.

All dose-response models will be re-fitted to the data (irrespective of statistical significance in the previous step) without any parameter assumptions to generate a set of new estimates of the model parameters. For all significant models, the generalised AIC will be calculated and reported in the displays. The final model will again be chosen as the model with the best fit (smallest AIC).

Estimates for each dose group will be calculated and will be based on the final dose-response model. No target dose criterion was pre-specified for the MRI-PDFP responder secondary endpoint.

Similar tables and figures will be used to display the results of the MCPMod analysis as were described in [Section 7.4.1](#).

The above analysis will be performed on the TS using both actual maintenance treatment and planned maintenance treatment. In both cases, all post-baseline MRI-PDFP data within the Week 48 visit window will be used, both on- and off-treatment.

MRI-PDFF continuous secondary endpoints - main analysis

Descriptive summaries of liver fat content (measured in units of % using MRI-PDFF), as well as absolute and percentage changes from baseline, will be presented over time. These will be produced on the TS for both actual maintenance treatment and planned maintenance treatment, and will include both on- and off-treatment data in the relevant visit windows. The

descriptive summaries will be produced overall, and further split by presence of any type of diabetes (Yes, No).

An MMRM will be fitted to the absolute change from baseline in liver fat content values (measured in units of % using MRI-PDFF) at each scheduled week (calculated as per [Section 6.7](#)). The MMRM will include fixed effects for baseline liver fat content (%) as a continuous linear covariate, and treatment, presence of diabetes of any type [yes, no], baseline fibrosis score [F1, F2, F3], visit, treatment by visit interaction and baseline by visit interaction as factors. The Kenward-Roger approximation will be used to estimate the denominator degrees of freedom.

Unstructured covariance will be assumed to model the relationship between pairs of measurements taken at different weeks on the same patient. If the model fails to converge, all reasonable attempts will first be made to encourage convergence on the specified model with all scheduled weeks included. These attempts will include (but may not be limited to) first adjusting singularity options, then increasing the maximum number of convergence iterations, using the Fisher scoring algorithm for the early iterations, removing multi-threading options, providing starting values for the covariance parameters, and excluding the fixed effect for baseline fibrosis score from the model. Only if none of these options is successful will simpler covariance structures be considered, in which case these will be evaluated in a nested sequence, where each covariance matrix is a special case of all which have been tried before.

Adjusted means will be calculated from the MMRM using the observed margins approach, in which the contribution of model factors to the estimate is weighted proportionally to the presence of these factors in the data.

A summary table will be produced of the MMRM results at each time point, including adjusted means and their standard errors for each treatment group, and including adjusted mean differences from placebo for each Survodutide dose group and their 95% confidence intervals.

Adjusted means from the MMRM will also be displayed graphically over time to assess the onset of effect over time.

The above analysis will be performed on the TS for both actual maintenance treatment and planned maintenance treatment, and will include both on- and off-treatment data in the relevant visit windows.

The MMRM analysis specified above will be repeated for percentage change from baseline in liver fat content values (measured in units of % using MRI-PDFF).

MCPMod analysis will not be performed for the continuous MRI-PDFF secondary endpoints.

Liver biopsy responder secondary endpoint

Frequency tables will be produced of the liver biopsy responder secondary endpoint (one stage decrease in fibrosis stage from baseline after 48 weeks of treatment) in both of the following ways:

- TS, actual maintenance treatment, using all post-baseline liver biopsy data within the Week 48 visit window, both on- and off-treatment
- TS, planned maintenance treatment, using all post-baseline liver biopsy data within the Week 48 visit window, both on- and off-treatment.

The above frequency tables will be displayed similarly to those for the primary endpoint.

A logistic regression model will be fitted to the liver biopsy responder secondary endpoint without an intercept, and will include presence of diabetes of any type [yes, no], baseline fibrosis score [F1, F2, F3] and the dose group as factors. In the case that 0 events are observed in any combination of dose group and strata, the Firth bias reduction method will again be used.

A summary table will be produced of the logistic regression results, including estimated odds ratios for the comparison of each Survodutide dose against placebo and their 95% confidence intervals and associated p-values.

The above analysis will be performed on the TS for both actual maintenance treatment and planned maintenance treatment, and will include both on- and off-treatment data in the Week 48 visit window.

MCPMod analysis will not be performed for the liver biopsy responder secondary endpoint.

[figure not shown]
Liver biopsy continuous secondary endpoint

[figure not shown]
Descriptive summaries of NAS total score from the liver biopsy, as well as absolute change from baseline, will be presented at Week 48.

Frequency tables will also be produced for each category of the NAS total score, and for each of the 3 NAS sub-scores (steatosis, lobular inflammation and ballooning) at baseline and at Week 48.

[figure not shown]
The descriptive summaries and frequency tables will be produced on the TS for both actual maintenance treatment and planned maintenance treatment, and will include both on- and off-treatment data in the relevant visit windows.

[figure not shown]

